## **8 Immunology Analyses**

Analyses will include both qualitative (responder rates) and quantitative outcomes.

Graphical displays of immune responses will include the following:

- 1) Serum IgG and IgA responses to LT and CS6
- 2) Antibody Lymphocyte Supernatants (ALS) responses to LT and CS6

Between-group comparisons will be examined with nonparametric tests (Kruskal-Wallis for continuous data and Fisher's exact test for categorical data) unless assumptions are fulfilled

for Analysis of Variance (ANOVA) or Pearson's  $\chi^2$ . Nonparametric paired *t* tests (Wilcoxon paired signed rank test) will be used to compare individual post-challenge to pre-challenge response within each treatment group unless assumptions are fulfilled for paired *t*-test. Comparisons of ALS responses post-vaccination will be performed using the Kruskal-Wallis test. All statistical tests will be interpreted in a two-tailed fashion using  $\alpha = 0.05$ . Statistical analyses will be performed using SAS v9.x for Windows (The SAS Institute, Cary, NC).

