### 3 Analytical Methods

For nominal outcomes, parameter estimates will be calculated with 95% confidence intervals utilizing valid asymptomatic and/or exact binomial estimates. For continuous outcomes, measures of central tendency will be estimated based on the data distribution. Data following a Gaussian distribution (or data for which the central limit theorem appear applicable) will be summarized across study groups using a mean and standard deviation (and/or 95% confidence intervals). Continuous data which are not normally distributed (or for which the central limit theorem is not applicable) and ordinal data will be summarized across study groups using a median and interquartile range. Data transformations will be applied to approximate a Gaussian distribution as applicable. In particular, titers will be log-transformed prior to statistical comparisons and log10-transformed means (and standard deviations) and/or geometric mean titers will be estimated.

In general, between-cohort comparisons will be examined with nonparametric tests (Kruskal-Wallis for continuous data and Fisher's exact test for categorical data) unless assumptions are fulfilled for Analysis of Variance (ANOVA) or Pearson's  $\chi^2$ .

Importantly, this study is designed to enable estimates of clinical, immunological, and microbiological endpoints not to compare parameter estimates across study cohorts. Nonetheless, these comparisons across cohorts will be made and guided by an Omnibus null hypothesis as follows (where  $\theta$  is any nominal, continuous or ordinal parameter):  $\theta_{\text{Cohort A}} = \theta_{\text{Cohort B}} = \theta_{\text{Cohort C}} = \theta_{\text{Cohort D}}$

Post-hoc comparisons will include the following: Bonferonni, Sidak, Tukey's HSD or Newman-Keuls.

Additionally, nonparametric paired *t* tests (Wilcoxon paired signed rank test) may be used to compare continuous data at two separate time points unless assumptions are fulfilled for paired *t*-test. Additional

comparisons may include repeated measures analysis of variance with study group as the between subject factor and sample collection time-points as the repeated factor.

All statistical tests will be interpreted in a two-tailed fashion using an  $\alpha = 0.05$ .

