### 6.2 Missing Data

All subjects selected to participate in the study and meet the necessary population requirements will be included in the safety and/or immunology analysis. Data will be assumed to be missing at random and missing data points will be excluded from analysis.

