### Results

**Table 3: Demographic characteristics of study subjects**

Characteristic	Participant (n =)	Screened (Not Enrolled)
Mean Age (sd)*	0	0
Age range	-	-
Gender (%)		
Male	0	0
Female	0	0
Race/Ethnicity		
African-American	0	0
Caucasian	0	0
Asian-American	0	0
Other	0	0

\*Measured in mean (standard deviation)

**Table 4:** Baseline characteristics of study participants (by cohort)

Cohort	A		B	C	D	E
	A-1	A-2				
Age a						
Gender [N (%)]						
Male						
Female						
Race/Ethnicity [N (%)]						
African-American						
White						
Asian						
Other						
LT IgA						
LT IgG						
CS6 IgA						
CS6 IgG						

a Presented as mean (standard deviation) or median (interquartile range)

**Table 5.** Safety profile of all adverse symptoms coded as ‘related’ to vaccine following vaccination [n(%)] (Groups compared using a Chi-squared analysis)

AE	Cohort A			Cohort B			Cohort C			Cohort D			Cohort E		
Dose	1	2	3	1	2	3	1	2	3	1	2	3	1	2	3
AE1															
AE2															
AE#															

**Table 6.** Safety profile of all adverse symptoms coded as ‘unrelated’ to vaccine following vaccination [n(%)] (Groups compared using a Chi-squared analysis)

AE	Cohort A			Cohort B			Cohort C			Cohort D			Cohort E		
Dose	1	2	3												
AE1															
AE2															
AE#															

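### No between-cohort titre comparison fixed in the SAP adjusts for baseline, although baseline titres are assayed and the cohorts are enrolled in sequence (minor)

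*SAP*

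**What the plan says.** - **Default test.** Section 8: "Between-group comparisons will be examined with nonparametric tests (Kruskal-Wallis for continuous data". The same sentence allows a switch if assumptions are met "for Analysis of Variance (ANOVA) or Pearson's" chi-square. For ALS there is no alternative: "Comparisons of ALS responses post-vaccination will be performed using the Kruskal-Wallis test".
- **Hypothesis.** Section 3 says that the study is meant for estimation and not for comparing cohorts, and then that "these comparisons across cohorts will be made and guided by an Omnibus null hypothesis as follows". That null is plain equality of cohorts. On level, Section 8 says "All statistical tests will be interpreted in a two-tailed fashion using" alpha 0.05.
- **Baseline data.** Section 8 (responder definitions) has pre- and post-vaccination sera assayed together. Section 9, Table 4, titled "Baseline characteristics of study participants (by cohort)", has rows for LT IgA, LT IgG, CS6 IgA and CS6 IgG.
- **Other uses of baseline.** Section 6.3 plans fold rises and seroconversion rates with confidence intervals. Section 8 plans paired within-group tests. Section 3 says that further comparisons may include "repeated measures analysis of variance with study group as the between subject factor and sample collection time-points as the repeated factor".
- **Design.** Section 5 describes open-label cohorts, each opened after safety review of the one before. Table 2 gives 5 subjects in each part of Group A and 10 in each of B to E.
- **Purpose.** Section 4.2 lists, as a secondary objective, finding a safe and immunogenic dose for a later challenge trial.

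**The concern.** In sequential, non-randomised cohorts, pre-vaccination titres can differ by chance or drift over the enrolment period. If post-vaccination titre depends on baseline, such a difference carries into an unadjusted comparison and can look like a dose effect or hide one. Adjustment also removes the part of the between-subject variance that baseline explains, which matters at 10 subjects per cohort. The covariate is already being collected.

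At stake is how cleanly the titre comparisons can inform the choice of dose for the next trial. Safety conclusions and escalation are unaffected, because Section 5 rests escalation on safety alone.

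**Working it through.** **The plan's own figure.** There is none to reproduce: the SAP states no power, SD or effect size for titres. The one interval in Section 6 concerns adverse events and has no bearing here.

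**Inputs.** From the SAP: 10 subjects in each of C, D and E; CssBA 5, 15 and 45 µg; two-sided alpha 0.05; log10 titres. Assumed: normal log10 titres, SD 0.5 (range 0.4 to 0.6), a step of 0.3 log10 per tripling of CssBA (0.6 log10 in all, about 4-fold), and baseline-to-post correlation r from 0 to 0.7. Section 8 does not say which continuous variable is compared across cohorts for serum; post-vaccination titre is taken here, as the SAP states for ALS.

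**Step 1: unadjusted tests.** The ANOVA noncentrality is n·Σ(μi − μ̄)²/σ² = 10 × (0.09 + 0 + 0.09)/0.25 = 7.2. On 2 and 27 degrees of freedom this gives 62% power. Simulation (4,000 replicates) gives 62% for ANOVA and about 58% for Kruskal-Wallis.

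**Step 2: omnibus ANCOVA.** Residual variance falls by the factor 1 − r². One degree of freedom goes to the covariate, and chance imbalance costs a factor of about 26/27. The noncentrality is then about (7.2 × 26/27)/(1 − r²), on 2 and 26 degrees of freedom.

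| r | 1 − r² | Noncentrality | Power, formula | Power, simulated |
|---|---|---|---|---|
| 0 | 1.00 | 6.9 | 60% | 60% |
| 0.3 | 0.91 | 7.6 | 64% | 64–65% |
| 0.5 | 0.75 | 9.2 | 73% | 73–74% |
| 0.7 | 0.51 | 13.6 | 89% | 88–89% |

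**Step 3: sensitivity to the assumptions (simulated power).**

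| Scenario | Kruskal-Wallis | ANOVA | ANCOVA, r = 0 / 0.3 / 0.5 / 0.7 |
|---|---|---|---|
| SD 0.4, step 0.3 | 78–79% | 82% | 81 / 84 / 91 / 98% |
| SD 0.6, step 0.3 | 42–43% | 46–47% | 45 / 49 / 56 / 75% |
| SD 0.5, step 0.2 | 28% | 31% | 29 / 32 / 39 / 54% |

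**Step 4: baseline drift with no dose effect.** Cohort baselines are shifted by 0, 0.5 and 1 SD. Rejection rates at nominal 5%:

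| r | Kruskal-Wallis, post titre | Kruskal-Wallis, fold rise | ANCOVA |
|---|---|---|---|
| 0 | 4–5% | 22% | 5% |
| 0.3 | 7% | 16% | 5% |
| 0.5 | 12–13% | 12% | 4–5% |
| 0.7 | 21–22% | 8% | 5% |

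Testing fold rise instead of post titre therefore does not solve the problem.

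**Step 5: dose trend (SD 0.5, r = 0.5).** With a linear response, a baseline-adjusted log-dose trend has 84% power, against 74% for omnibus ANCOVA. With a plateau (means 0, 0.5, 0.5) it has 66%, against 71%. With a hump (0, 0.6, 0.1) it has 4%, against 79% for omnibus ANCOVA and about 64% for Kruskal-Wallis. The gain depends wholly on the shape of the response.

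**The case against.** The strongest reply is that the SAP disclaims this use. Sections 3 and 6 say that the study is not designed to compare cohorts, escalation ignores titres, and nothing makes dose choice depend on a titre p-value. GMTs, fold rises and responder rates with confidence intervals already serve the dose objective. An omnibus test without covariates is a recognised choice. All of this stands and sets the severity. It does not remove the point, because Section 3 says that the comparisons will be made anyway, and adjusted GMT ratios serve estimation as well as testing.

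Several stronger readings are tempting but not supported:

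- **That the SAP ignores baseline.** It does not: fold rises, seroconversion, paired tests, Table 4 and the optional repeated-measures model all use it. What is missing is a fixed adjusted comparison between cohorts.
- **That Kruskal-Wallis is the only planned test.** ANOVA is allowed for serum titres when its assumptions hold. Under the normality assumed above, 62% is therefore the fairer comparator than 58%.
- **That the repeated-measures ANOVA would drop whole subjects.** Section 6.2 says "Data will be assumed to be missing at random and missing data points will be excluded from analysis". That excludes data points; no listwise deletion or estimation method is stated, and the model is optional.
- **That a trend test should replace the omnibus test.** Step 5 shows the risk when the response shape is unknown. A dmLT trend over A-1, B and C is weaker still: A-1 has 5 subjects, and 0 ng has no logarithm.
- **That adjustment removes bias.** It handles measured baseline titre only. Calendar-time and unmeasured differences between sequential cohorts remain.

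**Conclusion.** The point holds as a minor one. No fixed between-cohort titre comparison adjusts for baseline, although the data are in hand and the cohorts are not randomised. Under the central assumptions, adding baseline to the omnibus ANOVA changes power from 62% to about 64%, 74% or 88% at r = 0.3, 0.5 or 0.7. At r = 0 it costs 1 to 2 points. Under a baseline drift of up to 1 SD it holds the false-positive rate near 5%, where Kruskal-Wallis on post titres reaches 7% to 22% at r = 0.3 to 0.7.

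SD, effect, correlation and drift are all assumed. The correlation could well be low: Section 5.1.2 excludes recent ETEC or cholera exposure, and Section 8 sets titres below 5 to 2.5, so many baselines may sit at the floor and the gain would then be small.

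**What to change.** In Section 8, for serum titres:

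1. Add an ANCOVA on log10 post-vaccination titre at a named visit, with log10 baseline titre as covariate and cohort as factor. Report adjusted GMT ratios with 95% confidence intervals. State which cohorts enter, since the null in Section 3 names only A to D.
2. Keep the omnibus Kruskal-Wallis or ANOVA test as planned.
3. As supportive output only, pre-specify a log-dose CssBA trend over the cohorts that share one dmLT level: C, D and E, or B, D and E if D and E receive 100 ng.

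Because the trial is open-label, this should be fixed before titres are seen by cohort. The cost is SAP wording and modest programming, with no new data. The downsides are reliance on approximate normality of log10 titres, little gain or a loss of 1 to 2 points if baselines are at the floor, no protection against unmeasured time differences, and a trend test that fails on a non-monotone response.

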## **5 Study Methods**

This is an open-label Phase 1 clinical trial of CssBA±dmLT in which a total of 50 subjects will receive three vaccinations via IM injection on days 1, 22, and 43 (See Table 2). Dose escalation of CssBA from 5µg to 15µg to 45µg, and dmLT from 100 to 500ng will take place as outlined below. Group A is considered a pilot group in which CssBA and dmLT will be administered separately. All 3 doses will be administered and subjects monitored for safety 7 days after the third vaccination, prior to the enrollment of subjects in Group B.

The decision to advance to the next group will be based solely on the safety assessment. A dose level with no occurrence of stopping criteria will prompt moving to the next higher level. All safety data will be summarized and reviewed with the SRC prior to advancing to dose escalation.

Approximately one week after the first group (Group A) receives the third vaccination dose (Day 49), an interim Safety Report will be prepared by the PI and Study Statistician for review by the SRC. The content of the report will be agreed upon by the PI and the SRC and will include, but not be limited to, all adverse events (solicited, unsolicited, expected and unexpected) as well as relevant safety endpoints. Advancement to Group B will be based entirely on this safety assessment. The SRC's concurrence to advance to the next group will be made and provided in written format. This process will be repeated after groups B, C, and D before enrollment for the next group.

dmLT will be administered at the 500 ng dose in groups D and E if no significant reactogenicity is observed in Group C.

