### 6.3 Confidence Intervals and p-values

Rates of all AEs will be summarized with point estimate for percentage and 95% confidence intervals. Immunological outcomes will also be summarized in a tabular format and graphed to demonstrate kinetics of response. Qualitative (responder rates) and quantitative assessments (log transformed values) will be analyzed. Median increases (fold rises) of antibody concentrations and seroconversion rates will be calculated along with their 95% confidence intervals. Geometric mean titers will also be determined and presented with their 95% confidence intervals. All statistical tests will be interpreted in a two-tailed fashion using an  $\alpha = 0.05$ .

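### Computed exactly, the default within-group Wilcoxon test cannot reach p<0.05 in the two five-subject arms, and the SAP gives no criterion for switching to the paired t-test

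*SAP*

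**What the plan says.** SAP section 8 (Immunology Analyses) names the test for change within a group and its one exception: the Wilcoxon signed-rank test "will be used to compare individual post-challenge to pre-challenge response within each treatment group unless assumptions are fulfilled" for a paired t-test. The same paragraph sets the error rate: "All statistical tests will be interpreted in a two-tailed fashion using" alpha = 0.05. Section 3 (Analytical Methods) is more permissive: the signed-rank test "may be used to compare continuous data at two separate time points unless assumptions are fulfilled for paired" t-test. Neither section says how the t-test assumptions will be judged, or whether the Wilcoxon p-value is exact or asymptotic.

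Table 2 splits Group A into five subjects on CssBA 5 µg alone and five on dmLT 100 ng alone. Section 5 confirms the split: "Group A is considered a pilot group in which CssBA and dmLT will be administered separately". The shells in Tables 4, 7 and 8 report A-1 and A-2 on separate lines. Groups B to E have ten subjects each.

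Section 6.3 adds an interval for the median: "Median increases (fold rises) of antibody concentrations and seroconversion rates will be calculated along with their 95% confidence intervals". No method for that interval is named. Under section 6.2, "missing data points will be excluded from analysis". Sections 3 and 8 put the statistical comparisons of titres on the log10 scale.

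**The concern.** A rank test on five pairs has very few possible outcomes. If the most extreme of them is not below 0.05, the default test cannot detect a rise in A-1 or A-2, whatever the vaccine does. The answer in those arms then depends on two choices that the plan leaves open: when the t-test exception applies, and how the Wilcoxon p-value is calculated. The trial is open-label, and nothing in the SAP says that these choices are made before the titres are seen.

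A-1 and A-2 are the only single-component arms. If every subject responded in A-1 and in Group B, the default test would call the rise non-significant in one and clearly significant in the other because of group size alone.

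The quoted sentence in section 8 also compares samples before and after challenge. Section 5 describes three vaccinations and no challenge, and section 4.2 places challenge in a subsequent trial.

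**Working it through.** The SAP states no power or minimum p-value for this test, so there is no figure of its own to reproduce.

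**Inputs from the SAP.** n = 5 in A-1 and in A-2, n = 10 in B to E (Table 2); two-sided alpha 0.05 (section 8); missing points dropped (section 6.2), so n can only fall; log10 scale (sections 3 and 8).

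**1. Smallest exact signed-rank p-value.** Under the null hypothesis all 2^n sign patterns are equally likely. The most extreme two-sided result is all differences in one direction, so the minimum p is 2/2^n.

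| Pairs | Minimum exact two-sided p |
|---|---|
| 3 | 2/8 = 0.25 |
| 4 | 2/16 = 0.125 |
| 5 | 2/32 = 0.0625 |
| 6 | 2/64 = 0.03125 |
| 10 | 2/1024 = 0.00195 |

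Full enumeration gives the same values. Tied differences at n = 5 do not lower the minimum.

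**2. The same five-out-of-five result by the other routes left open.** The rank sum is 15, its null mean 7.5 and its variance 5 × 6 × 11/24 = 13.75 (SD 3.708).
- Normal approximation, uncorrected: z = 7.5/3.708 = 2.02, p = 0.043.
- Normal approximation, continuity-corrected: z = 7.0/3.708 = 1.89, p = 0.059.
- Paired t-test: significant if mean/SD of the log10 changes is at least 2.776/√5 = 1.24. For illustrative (assumed) log10 rises of 0.6, 0.9, 0.95, 1.2 and 1.5, the mean is 1.03 and the SD 0.338, so t = 6.81 on 4 df and p = 0.0024. Exact Wilcoxon on these values gives 0.0625.

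One data set can thus be called significant or not under the same text.

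**3. Can five pairs settle the t-test assumptions?** In simulation, a Shapiro-Wilk test at the 5% level on five values rejected exponential data in about 16% of samples and normal data in about 5%. A formal check would rarely detect even strong skewness.

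**4. Interval for the median fold rise.** The widest order-statistic interval, minimum to maximum, has coverage 1 − 2 × (1/2)^n. At n = 5 this is 1 − 2/32 = 93.75%; at n = 4 it is 87.5%. At n = 10 the second to ninth values cover 1 − 22/1024 = 97.9%, so B to E are not affected.

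**5. What the paired t-test offers at n = 5.** A 4-fold rise is log10(4) = 0.602. The SD of the log10 change is not in the SAP, so a range is assumed. Power comes from the noncentral t with 4 df and noncentrality 0.602 × √5/SD. The CI for the geometric mean fold rise runs from the estimate divided by, to the estimate multiplied by, 10^(2.776 × SD/√5).

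| Assumed SD | Noncentrality | Power | CI factor |
|---|---|---|---|
| 0.3 | 4.49 | 91% | 2.4 |
| 0.4 | 3.37 | 71% | 3.1 |
| 0.5 | 2.69 | 53% | 4.2 |

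**The case against.** Several arguments limit the point, and most of them stand.

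- **The t-test is already allowed.** A reader might infer that A-1 and A-2 would always be reported as showing no significant rise, or that power there is zero. The SAP does not support that. The same sentence permits a paired t-test, the log10 scale makes that route plausible, and an exact p-value is not prescribed. The limit applies to the exact Wilcoxon branch only.
- **No adjuvant claim is planned from these p-values.** A reader might infer that 0.0625 in A-1 against 0.002 in Group B would be presented as an effect of dmLT. The SAP compares groups by Kruskal-Wallis or ANOVA and Fisher's exact or chi-square tests, not by setting one within-group p-value against another. Also, only A-1 is a reference for what dmLT adds to the CS6 response, because A-2 contains no CssBA.
- **Not every readout is affected in a way that matters.** A rise is expected for CS6 in A-1 and for LT in A-2, which is four serum and ALS readouts per arm. Section 8 also assigns post-vaccination ALS comparisons to Kruskal-Wallis, so it is unclear how far the paired test covers ALS.
- **The median interval need not be distribution-free.** Section 6.3 does not ask for that. It names no method, however, and the usual order-statistic one falls short at n = 5.
- **Other summaries remain.** Responder rates and geometric mean titres with 95% CIs are reported regardless, and section 3 declares the study to be one of estimation.
- **The challenge wording is clerical.** The responder definitions in section 8 make the intended comparison of samples before and after vaccination clear enough.

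What these arguments do not remove is that the stated default cannot reject in two arms when computed exactly, and that the way out of it is not defined.

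**Conclusion.** The point holds in limited form. For the exact two-sided Wilcoxon test the minimum p is 0.0625 in A-1 and A-2 with all five pairs, and 0.125 with four, against 0.00195 with ten. Whether a rise in these arms is called significant rests on an undefined judgement about the t-test or on the choice of p-value approximation. An order-statistic 95% CI for the median fold rise is also out of reach at n = 5.

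The p-value and coverage limits depend only on n, alpha and sidedness as the SAP gives them. The t-test power and interval widths rest on the assumed SDs of 0.3 to 0.5 and on approximate normality of the log10 changes.

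Severity: should-fix. Immune response is a secondary objective, Group A is a pilot, and section 5 bases advancement solely on safety, so no primary result or escalation decision depends on these tests.

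**What to change.** In sections 3, 6.3 and 8 of the SAP:

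1. Pre-specify one within-group analysis for all cohorts: the geometric mean fold rise with a t-based 95% CI, and a paired t-test on log10 post-vaccination versus pre-vaccination titres.
2. Keep the Wilcoxon signed-rank test as a sensitivity analysis in the ten-subject groups, and state that its p-value is exact.
3. In A-1 and A-2, report the median fold rise with its range and no 95% CI.
4. Show individual fold rises alongside the summaries.
5. Replace challenge with vaccination in the section 8 test sentence and in the serum and ALS responder definitions.

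The cost is SAP wording only; no samples, visits or subjects are added. The downside is reliance on approximate log-normality at n = 5. Section 8 assigns 2.5 to reciprocal titres below 5, which may bunch the baseline values and strain that assumption. Item 4 lets a reader see whether it does.
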